6.2.2 Enrollment, Randomization and Baseline assessment

Clinical Assessments: *will be repeated as per the Assessment table (attached)*. Those who continue to meet the inclusion criteria at screening, and agree to participate in the study, will be scheduled for a baseline assessment (baseline 2) that will include assessment of depression severity that will be scheduled within 2 months of starting the interventions.

Randomization

After all screening and baseline test results are reviewed and eligibility criteria are confirmed, subjects will be randomized to two groups if patients continue to meet eligibility criteria and sign the informed consent form. The anticipated waiting time from screening to randomization to the initiation of the interventions is up to 3-4 months.[\[NCCIH1\]](#) All eligible subjects will be randomized to the TCC, or HEW control group using a computer-generated random assignment scheme, which assigns subjects in a 1:1 ratio to each group using a customized module built into the centralized data system. Randomization will be stratified by site and by whether the subject will receive imaging or not. Specifically, there will be four strata for randomization defined by the 2 x 2 combinations of site (UCLA or MPTF), with approximately 60-70% of the subjects being recruited at UCLA and the remainder at MPTF, and imaging (yes or no). Within these strata, class sizes of 6 or 7 will be randomized to TCC or HEW.[\[NCCIH4\]](#) Access to the data system, including the randomization program, is controlled via a hierarchical system of password protected logins, ensuring that study personnel can view only the parts of the system that are appropriate for their role. This helps to maintain blinding and ensure subject confidentiality. Careful security protocols will also be maintained prior to the entry of data into the online system. Specifically, paper copies of patient study forms will be stored in locked file cabinets and will be accessible only to authorized personnel. A shredder will be used to discard all unwanted study documents.

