5. STUDY INTERVENTIONS

5.1 Interventions, Administration, and Duration

Each class will be held for 60 minute per day/week. Homework assignments will be equal in all groups and ask for at least 20 minutes of either TCC, or computer searches on the topics of wellness at home. Participants will be asked to keep diaries of daily exercises, time spent and adherence to the tasks will be compared between the groups, and used as a predictor/mediator in the primary analyses of response. All classes will be offered once a month as booster session for the remainder of the study between weeks 12 and 24. Subjects will be given a DVD of the training course and encouraged to continue practice at home. Subjects in the HEW group will be asked not to join any of the TCC classes until the end of the study. At the end of the study, participants will be offered an option of participating in the two alternative classes.

Tai Chi Chih (TCC): TCC employs “meditation through movement” as a means of helping older adults cope with fatigue, perceived physical limitations, and negative emotional states, which are commonly associated with insomnia. Patients will be informed that TCC constitutes a health management intervention, which incorporates meditation and physical activity to promote a sense of well-being and control over negative symptoms associated with depression. The standard detailed protocol for TCC uses an adapted protocol from the “Tai-Chi-Chih Joy through movement” by Justine F. Stone¹⁴¹ and has been used in several studies by our research group, and others (i.e., R21-AT002307). TCC sessions will be held for 60 min a day once a week. Each class will allow 10 minutes of warm-up (e.g., stretching, breathing), 5 minutes of cool down. Participants will be instructed to practice at home for 20 minutes per day using handouts and documenting their practice in their daily diaries.

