Health and Wellness Education (HEW) control group: This condition will serve as an active control for nonspecific treatment elements such as attention and group support that pose rival explanations for the effectiveness of TCC. Participants will be informed that this intervention is designed to help reduce the severity of depressive symptoms, and all participants will be offered a choice of TCC in the end of the interventions, to balance expectations for the TCC intervention; therefore, reducing the placebo effect. The PI and trained study staff will implement HEW using a manual that will present educational information and describe learning objectives and patient activities to promote integration of material. The detailed protocol for Health Education has been developed and used in the pilot project. The HEW sessions will be held once a week for 60 minutes over the 12-week treatment period. We will follow a didactic format, inviting experts to lecture on key topics, followed by focused group discussion, and post-discussion self-help quizzes to assess patient learning. This novel use of a non-exercise control intervention, which matches the exercise intervention in duration, frequency and social contact, represents an important methodological advance.¹⁴³ Participants will be instructed to practice at home in computer searches addressing the health topics discussed in the session for 20 minutes per day. Weekly supervision by [name] with project health education instructors will be used to monitor instructors’ adherence to the educational protocol. Tai Chi Chih trainers will follow the same manual. We will contact Tai Chi Chih Association for an opportunity to monitor TCC trainers’ adherence to the manual protocol. Participants will be asked to keep diaries of exercise or computer searches and the adherence will be compared between the groups.

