Visit 4. Baseline visit will be performed within 2 months prior to initiation of the interventions with assessment of mood and vital signs (30 min)

Follow-Up Visits (Visits 4-9 and 12-13): Follow-up assessment will occur bi-weekly (every 2 weeks) for 12 weeks and then monthly in order to ensure safety. Each visit will last approximately 30 minutes. Interviews and questionnaires will be used to determine if the treatment is working and useful. Adherence will be monitored at each visit. At each follow-up visit, vital signs will be measured (5 minutes), practice and homework log will be reviewed, and questionnaires will be administered (25 minutes).

Weekly Tai Chi or Health and Wellness Education (12 classes): Weekly Tai Chi or health and wellness education training will occur every week for 60 minutes for 12 weeks. The weekly sessions will last approximately 60 minutes per class. Homework adherence and diaries will be monitored at each class.

Visits 10/11 and 14-19- Outcomes and Endpoints. 12 week follow-up visit (Visit 10/11): During the final visit, a physical, psychiatric examination, and a follow-up blood draw for genetic analysis will be repeated. MRI will be repeated at 12 weeks. The follow-up visit 12 will be split in 2 visits (for clinical, cognitive, laboratory, and MRI) will last 4 hours (1 hour MRI). The 6-month follow-up

visit (14/15) will be approximately 1.5 hours. Both the 12- or 24-month follow-up visit will be split in 2 visits (for clinical, cognitive, laboratory, and MRI) will last 4 hours (1 hour MRI). The Month 12/24 visit will be completed by only those participating in the MRI portion of the study. Since this visit was added onto the original study, some of the participants may have passed their Month 12/24 time point. We will allow this visit to occur any time succeeding the Month 12 mark, and will note the visit type by proximity of their timeline (ie: Participant completes visit at Month 17, would be assigned to Month 12 Visit).

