Aim 1: Primary analysis: Our primary analysis will consist of a GLMM for HAMD-24 with treatment group effects and time main effects, along with two-way interactions of time and group. The primary analysis will assess treatment effects at the end of treatment at 12 weeks. Our primary analysis is valid under the assumption of missing-at-random. To study missingness patterns, we will compare mean response trajectories of the primary outcome measure HAMD for subjects who dropped out and those who did not. We will further compare treatment groups for drop-out rates, time to drop-out and drop-out reasons. Since it is theoretically impossible to rule out data missing-not-at-random, we will also perform sensitivity analysis taking a pattern mixture approach. Our pattern mixture approach will make assumptions on how the outcome trajectory

for subjects who dropped out will differ from those for subjects who did not. These differences will be allowed to be vary across treatment arms and the amount of difference will be varied in a plausible range to obtain a full sensitivity analysis.

Secondary analysis: Treatment maintenance will be assessed via the GLMM at follow-up as part of the secondary analysis. Secondary analysis will also include comparison of remission status (binary outcome) at the end of treatment between treatment groups via a logistic regression. Analyses for secondary outcomes clinical global improvement (CGI) and cognitive domain scores in the executive function and memory domains will be similar to those above for the continuous HAMD scores. As noted in the Neuropsychological Assessment section, there are 4 cognitive domains that are being assessed. Of these, the two primary cognitive domains of interest for this proposal are executive function and memory. A separate GLMM as above will be estimated using these 2 domain scores as dependent variables. In addition treatment adherence and time in practice will be considered as moderators of treatment effects in the longitudinal modeling of primary depression and imaging outcomes in the first two aims.

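### Both interventions are taught in classes of 6 or 7, but no planned analysis has a class term; class effects on 12-week change that are specific to each arm would make the primary interval too narrow

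*Combined protocol and SAP*

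**What the plan says.** **Delivery.** Section 5.1 states that "TCC sessions will be held for 60 min a day once a week". HEW follows the same weekly 60-minute pattern, with lectures "followed by focused group discussion". Section 6 confirms for both arms that "training will occur every week for 60 minutes for 12 weeks".

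**Randomisation.** Section 6.2.2 states "All eligible subjects will be randomized to the TCC, or HEW control group", using a scheme that "assigns subjects in a 1:1 ratio to each group". After defining the four site-by-imaging strata it adds "Within these strata, class sizes of 6 or 7 will be randomized to TCC or HEW". The first two statements make the subject the unit; the third can be read as making it the class.

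**Analysis.** Section 9.6, Aim 1, specifies a "GLMM for HAMD-24 with treatment group effects and time main effects, along with two-way interactions of time and group", with the treatment effect assessed at 12 weeks. The only correlation that section 9.6 says the model handles is between repeated measurements on one subject. Remission at end of treatment is compared by logistic regression between arms.

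**Power.** Section 9.2 reports a detectable difference of 0.32 SD from 99 completers per arm, seven visits and a correlation of 0.5 between visits. No ICC or design effect is stated.

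**Nearest provisions.** Section 6.2.3 promises control for instructor if several teach. Section 9.2 leaves the covariance structure to a likelihood ratio test or AIC. Section 9.6 leaves covariates open, with demographic and illness-course variables as examples. None of these names class.

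**The concern.** People who share an instructor, a timetable and a discussion group for 12 weeks may improve by more similar amounts than people in different classes. The plan itself treats attention and group support as active non-specific elements. If such similarity arises separately within each arm's classes, the arm difference in change carries between-class variance that the planned model does not count. The standard error is then too small, the nominal 5% test rejects too often, and the 95% interval covers less than 95%.

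This concerns the primary HAMD-24 comparison at week 12 and, to a lesser degree, remission. It can arise even if subjects are individually randomised, because the clustering comes from shared teaching after assignment. If whole classes are randomised, any class-level variation in change counts, including variation present before teaching starts.

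**Working it through.** **Inputs from the documents.** 220 subjects, 1:1; class size 6 or 7 (6.2.2); visits at weeks 0, 2, 4, 6, 8, 10 and 12; correlation 0.5; 99 completers per arm; 80% power; alpha 0.05; stated d = 0.32; pilot effect 0.65 (all 9.2).

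**Assumptions.** Two-sided test; compound symmetry; full classes averaging 6.5; ICC defined as the class share of variance in 12-week change, ranged over 0.01 to 0.10.

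**1. Reproduce the plan's figure.** With the time range scaled to 1, the sum of squares of the seven visit times is 0.7778. The variance of one subject's fitted change is (1 − 0.5)/0.7778 = 0.643 SD². The SE of the arm difference is √(2 × 0.643/99) = 0.1140, and the detectable d is (1.960 + 0.842) × 0.1140 = 0.319. This matches 0.32 with independent participants. An ICC up to ((0.325/0.3193)² − 1)/4.82 = 0.0075 would also round to 0.32, so the match does not by itself exclude a very small allowance; none is stated.

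**2. Classes.** 220/6.5 is about 34 classes, 17 per arm. Completers per class: m = 99/17 = 5.82.

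**3. Effect of ignoring class.**
- Design effect, both arms clustering: DE = 1 + 4.82 × ICC. One arm only: DE = 1 + 4.82 × ICC/2.
- Type I error = 2 × (1 − Φ(1.96/√DE)).
- Interval ratio = √DE.
- Detectable d = 0.319 × √DE.
- Power at 0.32 = Φ(0.32/(0.1140 × √DE) − 1.96).

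| Assumed ICC | 0.01 | 0.02 | 0.05 | 0.10 |
|---|---|---|---|---|
| DE, both arms | 1.048 | 1.096 | 1.241 | 1.482 |
| Type I error | 5.6% | 6.1% | 7.9% | 10.7% |
| Correct interval wider by | 2% | 5% | 11% | 22% |
| Detectable d | 0.33 | 0.33 | 0.36 | 0.39 |
| Power at 0.32 | 78% | 76% | 71% | 64% |
| Type I error, one arm only | 5.3% | 5.6% | 6.4% | 7.9% |
| Interval wider, one arm only | 1% | 2% | 6% | 11% |

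**4. Simulation, 17 classes of 6 or 7 per arm, 99 of 110 kept at random.** A seven-visit slope test ignoring class, with separate class effects on change in each arm, gave 5.7 / 6.1 / 8.1 / 11.3%. With a class effect constant over time it gave 5.0 to 5.2%, because such an effect cancels from the group-by-time contrast. A class-means test on change, with separate effects, held about 5%.

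**5. Variation shared by concurrent TCC and HEW classes, subjects individually randomised.** Type I error on 12-week change, ignoring class, was about 4 to 5% over the same ICC range. The shared part cancels from the arm difference and only inflates the residual variance.

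**6. Remission.** Logistic comparison without class, assumed remission 33% (section 2.2 cites 30–35% in antidepressant trials), same ICC values on a latent scale. Separate effects per arm: 5.2 / 5.5 / 6.5 / 7.9%. One arm only: 4.9 / 5.1 / 5.8 / 6.4%. Shared effects: 4.4 to 4.8%.

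**7. Pilot effect.** Power at 0.65 with ICC 0.10 is Φ(0.65/(0.1140 × 1.2175) − 1.96) = 99.7%.

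**The case against.** **The condition is narrow.** A reader might infer that any variation in change between classes invalidates the primary interval. It does not. Step 5 shows that variation common to concurrent classes in both arms, such as season or site, leaves the test slightly conservative under individual randomisation. Most of section 6.2.2 describes individual randomisation, so this case is realistic. This objection stands and limits the claim to arm-specific effects.

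**The trial is not shown to be cluster-randomised.** The sentence on class sizes invites that reading, but the statements around it assign subjects. The text needs clarifying; it does not settle the matter.

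**The size is unknown.** No document gives an ICC, and at 0.01–0.02 the effect is small. TCC subjects are told "Participants will be instructed to practice at home for 20 minutes per day", HEW has equal homework, and section 5.5 allows remote participation; all of these may weaken class effects. The 17 classes per arm also assume that classes fill. This stands, but without a recorded class the trial could not show that the ICC is negligible.

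**Power is adequate.** A reader might infer that the trial is underpowered. Section 9.2 calls its figure conservative because the model uses all observed data. If all 110 per arm were fully informative, power at 0.32 would be 82 / 80 / 75 / 66%, so the stated 80% can hold up to an ICC of about 0.02. Power at the pilot effect is not in doubt.

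**The plan has relevant provisions.** The instructor sentence is conditional, gives no method, is not carried into section 9, and concerns instructor, not class. Section 6.2.3 also indicates that the two interventions have different instructors, so fixed instructor effects would be aliased with treatment unless constrained or averaged over. Covariance selection is described beside the correlation between time points. These show that the model is not fully fixed, but they do not supply a class term.

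**Conclusion.** The omission is certain: group delivery is explicit, and no class term appears in the primary model, the remission model or the power calculation. The consequence is conditional. If change varies between classes separately within each arm, or at class level in any way when whole classes are randomised, type I error for the primary test is about 5.6% to 10.7% over an assumed ICC of 0.01 to 0.10, with correct intervals 2% to 22% wider. One-arm clustering roughly halves this; time-constant effects, or effects shared across arms under individual randomisation, remove it. Remission is affected less.

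The figures rest on an assumed ICC range, 17 full classes and 99 completers per arm. The concern is validity of the test and interval, not power at the pilot effect. Severity is minor to should-fix: small at ICC 0.01–0.02, but on the primary inference and cheap to address.

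**What to change.** 1. In 6.2.2, state whether the subject or the class is the unit of randomisation.
2. Record a class identifier for every participant, including remote classes (5.5).
3. In 9.6, add a class-level random effect on change (class-by-time), nested in arm, with small-sample degrees of freedom. State a fallback for a class variance estimated at zero: a cluster-robust variance with small-sample correction, or a class-level test. The fallback matters because a simple moment estimate was zero or negative in 44% of simulated trials at ICC 0.01 and 36% at 0.02. The random-effect model itself was not simulated here.
4. Account for class in the remission model.
5. If instructor is modelled, treat it as random within arm.
6. In 9.2, restate the detectable effect over a stated ICC range: about 0.33 to 0.39 SD for ICC 0.01 to 0.10. No extra enrolment is proposed.

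**Cost.** SAP wording and one variable, recorded or recovered from class lists. Intervals become about 2% to 22% wider depending on the ICC. A class-level test on 32 degrees of freedom is about 4% wider even at ICC 0 (t/z = 1.039), and it is conservative if class effects are shared across arms.

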6.2.3 Blinding

We have considered different options for blinding/masking procedures. We will provide treatment groups that both incorporate “exercise and wellness education,” which we believe will generate equal expectations for benefit. Both groups will be informed that they will receive exercise and education upon consent and entry into the study. Each group will have an option of trying and switching to the two other interventions after up to 24 months of follow up, which facilitates blinding and controls for the exercise effect. For ethical reasons, we cannot have a “usual care” group in which older depressed subjects at high risk for worsening of depressive symptoms in the absence of behavioral treatment. All subjects will be blind to the fact that symptomatic, functional and cognitive improvement are the outcomes of interest, and the differences in the interventions, since all participants will be recruited to receive a “wellness and exercise treatment program.”

Blind Assignment: The trained behavioral raters will also be “blind” to the treatment assignment.

Both statisticians and the PI will be blind to the group assignment. Only trainers and study coordinators will be unblinded, but they will not have access to the data monitoring or analyses. Database staff entering the data or managing the data will be blind to the treatment assignment. Groups in the documentation will be identified as 1 and 2. If unblinding occurs in the process of assessment, we will assign different raters who will continue to be unaware of the treatment group, and will re-establish reliability on all assessment instruments. We will minimize potential “placebo effects” by balancing expectations by introducing two “wellness and exercise” interventions for depression. We will measure and compare the expectancy for the outcomes at baseline, Week 12, Month 6 and Month 12 as specified below (or Month 24 if 12 months have passed). Both classes will be taught by different instructors. We will control for the “instructor” effect if several instructors teach classes.

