2.2 Study Rationale

Rationale for duration of interventions and follow-up, and masking procedures: 1) The proposed study uses some elements of the design used in our R21 pilot with novel features of not using psychotropic drugs, double-blind assignment and masking procedures to treatment groups, and the 2 active control conditions to assess the effects of the interventions on the improvement in primary and secondary clinical outcomes, and biomarkers. Based on our pilot study, participants needed 12 weeks to learn and master TCC and thus a 12-week duration is necessary for the active treatment trial.

The post-intervention follow-ups *will include all participants including those who could show worsening of symptoms and discontinue the study* to follow and compare the effect of TCC versus HEW to explore the role of biomarkers as predictors and moderators of the response. Those who agree to follow-up and do not demonstrate response or show worsening will be encouraged to seek treatment alternatives that will be documented in the chart and controlled for in analyses (e.g. types of treatments, dose, and duration). Most participants will be treated in UCLA clinics and their treatment records will be available for review of response patterns. *Follow-up of 6 and 12 months (or 24 months if 12 months have passed) will allow us to document maintenance of symptoms improvement, relapse of major depressive episodes, and compare the rates of maintained remission between the groups, as well as predictor/moderator effects of the biomarkers.*

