11.2 Informed Consent Forms

A signed consent form will be obtained from each participant (Appendix A). For participants who cannot consent for themselves, such as those with a legal guardian (e.g. person with power of attorney), this individual must sign the consent form. The consent form will describe the purpose of the study, the procedures to be followed, and the risks and benefits of participation. A copy will be given to each participant or legal guardian and this fact will be documented in the participant's record.

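### Section 6.2.3 has both arms told they will receive exercise and claims participants are blind to outcomes and arm differences; section 5.1 contradicts both, so the trial is assessor-blinded, not double-blind

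*Combined protocol and SAP*

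**What the plan says.** **Masking text.** Section 6.2.3 (Blinding) says: "Both groups will be informed that they will receive exercise and education upon consent and entry into the study". On what participants know, it says: "All subjects will be blind to the fact that symptomatic, functional and cognitive improvement are the outcomes of interest". The same sentence extends that blindness to how the interventions differ. On expectation it says: "We will minimize potential “placebo effects” by balancing expectations by introducing two “wellness and exercise” interventions for depression". Section 2.2 lists among the novel features "double-blind assignment and masking procedures to treatment groups".

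**Intervention text.** Section 5.1 describes the control arm as follows: "This novel use of a non-exercise control intervention". Its content is expert lectures, group discussion and quizzes, with 20 minutes a day of computer searching on health topics as homework. Of HEW it says: "Participants will be informed that this intervention is designed to help reduce the severity of depressive symptoms". Of the other arm it says: "Patients will be informed that TCC constitutes a health management intervention". That TCC sentence goes on to name meditation, physical activity and control over symptoms that accompany depression. HEW participants are asked to keep out of TCC classes until the study ends, and everyone is offered TCC later.

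**Protections already planned.**
- Outcome raters are blind, and are replaced if unblinded (6.2.3; see also 6.2.4).
- Credibility and expectation are rated after the second session and post-intervention (5.2).
- Expectancy is compared at baseline, week 12, month 6 and month 12 (6.2.3).
- Drop-out rates, timing and reasons are compared by arm, with a pattern-mixture sensitivity analysis (9.6).

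**The concern.** The masking section and the intervention section describe two different control arms and two different states of participant knowledge. Two things are at stake.

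The first is disclosure. A participant assigned to HEW under the 6.2.3 wording is told to expect exercise that the class does not contain.

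The second is what the trial may claim. HAMD and MADRS ratings depend partly on what the participant tells the rater, and section 6.2 describes the GDS as a self-assessment. If participants know which class they attend and believe one is more likely to help, a blind rater does not screen that out. A report that calls the trial double-blind would tell readers the result is protected on the participant side when it is not. Section 5.2 itself treats equal credibility of the two arms as essential, so the plan sets this standard for itself.

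**Working it through.** No figure in the plan is at issue, so the check is a comparison of the text.

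| Question | Sections 6.2.3 and 2.2 | Section 5.1 |
|---|---|---|
| Does HEW contain exercise? | Yes: both arms are called wellness and exercise interventions | No: a non-exercise control with lectures, discussion, quizzes and computer searches |
| Do participants know that mood is a target? | No: blind to symptomatic improvement as an outcome | Yes: HEW is presented as reducing depression severity, TCC as giving control over depression-related symptoms |
| Do participants know how the arms differ? | No: blind to the differences | Yes: TCC participants hear of meditation and physical activity; HEW participants are asked not to join TCC classes and know TCC is offered later |

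1. **Exercise.** Neither section 5.1 nor the earlier account of the interventions (Interventions and Duration) gives HEW any exercise during the 12 weeks. Section 9.6 places the primary comparison at week 12. Over that period the statement quoted from 6.2.3 is therefore untrue for HEW. With 220 participants assigned 1:1, it applies to 220 / 2 = 110 planned participants.

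2. **Blind to outcomes.** The primary outcome is change in HAMD (9.5.1), a measure of depressive symptom severity. Section 5.1 tells participants in both arms that their class bears on depressive symptoms. The outcome-blind claim in 6.2.3 cannot stand beside that.

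3. **Blind to differences.** A person who attends lectures knows that they are not doing a movement class. A person asked to keep out of TCC classes knows that another class exists. At most, participants could be kept unaware of which arm the investigators expect to do better, and that is not what 6.2.3 claims.

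4. **Label.** Steps 2 and 3 leave rater blinding in place and remove the participant side. The design described in 5.1 is assessor-blinded.

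5. **Protections.** Blind raters limit rater bias. The drop-out comparison and the pattern-mixture analysis address differential loss. Neither acts on an expectancy shift in scores that are observed. Credibility and expectancy are measured, and 6.2.3 says expectancy will be compared, but section 9 names no analysis that uses either. The Appendix A schedule also has no expectation rating near the second session, although 5.2 asks for one.

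**The case against.** The strongest reply is that the exercise wording is stale text rather than the operative script. Several sentences seem to come from a design with an additional, exercise-based control. Section 2.2 refers to two active control conditions and, under Innovation, to a comparable exercise that does not generate chi. Section 6.2.3 itself speaks of switching to two other interventions. The sentence in 2.2 that carries the double-blind label also lists the absence of psychotropic drugs, although the population is on stable antidepressant treatment or psychotherapy. This explanation is plausible, and it makes the point an internal inconsistency rather than a deliberate choice. It does not remove the point, because 6.2.3 is the current masking section and would be followed as written.

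The plan also deserves credit for blind raters, expectancy ratings and the missing-data analyses. As shown in the working, they reduce the exposure without supplying a participant blind.

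A reader might infer more than this. Four stronger readings are not supported:
- **That HEW participants suffered a broken promise.** The consent pages are not available, so what was actually said cannot be seen. TCC is offered to everyone later, so exercise is deferred rather than denied, although the timing is given variously as the end of the interventions, the end of the study and up to 24 months.
- **That the arms are told different purposes, depression for HEW and general health for TCC.** This comes from stopping the TCC sentence early. Read in full, it also refers to depression.
- **That disappointment lowers expectation and raises drop-out in HEW only, with a bias of some stated number of SDs.** The documents give no expectancy gap and no link from expectancy to HAMD. Multiplying an assumed gap by an assumed correlation would also treat the association as wholly causal.
- **That the consent form reveals the outcomes.** Section 11.2 says only "The consent form will describe the purpose of the study", which is standard wording and does not show that outcomes or hypotheses are disclosed.

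**Conclusion.** The point holds as a contradiction with consequences. Sections 2.2 and 6.2.3 claim a participant blind that the interventions in section 5.1 rule out, and 6.2.3 plans a statement to HEW participants that is untrue for the 12-week primary period. The finding about the blind rests on the text alone. The finding about the statement assumes that 6.2.3 is followed as written.

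Its reach is the planned 110 HEW participants for the inaccurate statement and the whole trial for the double-blind label. Participant expectancy remains a possible influence on HAMD, MADRS and GDS. Its size cannot be derived from the documents, and its presence is not shown by them. The conclusion concerns what participants are told and what the trial can claim, not a demonstrated bias in favour of TCC.

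**What to change.** - **Section 6.2.3, statement to participants.** Replace the statement that both groups will receive exercise with one accurate statement used for both arms. For example: assignment to one of two 12-week group wellness programmes, both of which may help mood. Bring the other phrases in the section that call both arms exercise interventions into line.
- **Section 6.2.3, blinding claim.** Delete the claim that participants are blind to the outcomes and to the differences between interventions.
- **Sections 2.2 and 6.2.3, label.** Describe the trial as assessor-blinded, with participants aware of their class.
- **Reporting.** Present the GDS as an unblinded self-report.

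The arm-specific descriptions in section 5.1 need not be removed. They support the credibility of HEW, and dropping them would be a trade-off rather than a correction.

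The cost is revised wording and IRB approval of it, with no added procedures. The trial can no longer be called double-blind.
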